The primary objectives of this study are to compare the therapeutic impact of liraglutide 368 3 mg versus placebo on reduction of body weight and biochemical hyperandrogenism (as 369 determined by the free androgen index) in obese non-diabetic women with PCOS. We will 1) 370 determine the percentage of participants achieving \geq 5% reduction in baseline body weight with 371 each treatment and 2) assess the inhibition of biochemical hyperandrogenism (ovarian androgen 372 production and sex hormone binding capacity) in response to each treatment.

373 Secondary study objectives

The secondary study objectives are to determine the effect of treatment with antiobesity medication versus placebo on anthropometric, **clinical**, hormonal and metabolic parameters in non-diabetic obese women with hyperandrogenism.

377

378 EFFICACY VARIABLES/MEASURES

379 *Primary endpoints*

The co-primary end points are to compare obese women with PCOS receiving liraglutide 3mg (LIRA 3 mg) with those receiving placebo on body weight and bioavailable ovarian androgen

- 382 concentrations as determined by:
- 1a. percent change in body weight from baseline to week 30 and
- 1b percentage of participants achieving ≥5% reduction in body weight from baseline
 to week 30
- 3862reduction of free androgen index [FAI=testosterone (T)/sex hormone binding387globulin (SHBG) levels] from baseline to 30 weeks
- 388 Secondary endpoints
- 389 We will further examine the impact of the administration of these pharmacotherapies in obese
- 390 non-diabetic PCOS women on:
- 391 Anthropometric and Clinical Indices
- Change from baseline of body mass index [BMI], absolute body weight, waist circumference (WC), waist: hip ratio (WHR), waist-height ratio (WHtR), and whole-body dual-energy X-ray absorptiometry [DXA]) measures of body composition (trunk fat mass and truck fat/extremities fat ratio) to determine the relative contribution of changes in fat mass (FM) vs. lean mass (LM) to overall weight loss at week 30
- 2. Compare women with hyperandrogenism for frequency of patients achieving a body
 weight reduction of at least 10% [Time Frame from baseline to 30 weeks]
- 399 3. Change in menstruation frequency (normalized to the number of menstruations per year) from before and after 30 weeks of treatment
- 401 Metabolic Parameters
- 402 1. Change in glycemic values from baseline to 30weeks
- 403 2. Fasting and 2 hour glucose levels after an OGTT

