Up to 92 non-diabetic women with PCOS, aged 18 years to 45 years of age, meeting BMI 451 criteria, will be invited to participate. We will define hyperandrogenism using biochemical 452 453 evidence (elevated testosterone and/or free androgen index with exclusion of androgen secreting tumors). Subjects will be recruited using flyers distributed in the metabolic clinic, 454 455 gynecology clinics and pathology laboratory associated with Woman's Hospital. All participants will be provided a written informed consent and be asked to sign a copy before being enrolled in 456 457 the study. The Woman's Hospital Institutional Review Board (WHIRB) will have approved both the protocol and consent. All subjects will undergo a verbal screen, and if they are eligible and 458 459 sign a medical release form, their medical records will be obtained to confirm their medical history. All subjects will provide a medical and gynecological history including assessment of 460 regularity and length of the menstrual cycle, with recording of menses in the 12-month period 461 before the study. Patients will be specifically asked about the number of menses in previous 12 462 463 months (menstrual frequency). To be eligible for the study, subjects will be required to have 464 irregular periods (cycle length outside 24–35 days or <8 cycles per year). All enrolled patients will then undergo baseline clinical and laboratory evaluations to exclude diabetes, thyroid 465 466 disorder, significant hyperprolactinemia, elevated liver enzymes and/or severe hypertriglycidemia. A negative serum pregnancy test is a prerequisite for commencing 467 468 treatment. Subjects will be instructed to use an IUD or double barrier methods of contraception (unless sterilized) during the study since hormonal methods are not permitted. Glycemic status 469 470 will be measured at the beginning and end of each treatment period by a standard 75g oral 471 glucose tolerance test (OGTT). Obese women who meet study eligibility criteria (see inclusion and exclusion criteria) will be eligible to be randomized to treatment. We anticipate that 72 472 473 women will be randomized to treatment (this allows for 20 women to fail screening). Exclusion 474 criteria include any condition, which in the opinion of the investigator would place the subject at 475 increased risk or otherwise make the subject unsuitable for participation in the study.

- 476 Key Inclusion Criteria
- 477 Female gender
- 478 18-45 years of age

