During the study period, cycle control will be assessed daily by the subjects using a menstrual diary. Vaginal bleeding will be classified by the subject as either spotting (requiring at least one pad/tampon per day) or bleeding (two or more pads/ tampons per day). The effects of treatment intervention on menstrual abnormalities will be evaluated by assessing posttreatment changes in menstruation frequency over 30 weeks from the patient's menstrual cycle diary and normalized to the number of menstruations per year (52 weeks).

All side-effects will also be recorded and summarized for the 30 week-treatment period. During the whole study period, compliance to the treatment will be documented. Compliance with treatment will be checked by questioning about the side-effects and a subjective evaluation of the tolerability of the administered drug; the patients will also asked about incidental missed administrations and whether they had correctly followed the scheduled treatment. Questioning regarding the occurrence of adverse events and use of concomitant medication will take place throughout the trial.

655

656 Study Medication

657 Study Drug Storage- All investigational products (study drugs) will be stored under 658 appropriate storage conditions in a secure area according to local regulations. The investigator is responsible for ensuring that it is dispensed only to study subjects and only from official study 659 660 sites by authorized personnel, as dictated by local regulations. The investigator is responsible for 661 ensuring that the investigational product is stored under the appropriate environmental 662 conditions (temperature, light, and humidity), as noted in the product labeling. Novo Nordisk 663 will supply all investigational products. The distribution of all supplied medications is the 664 investigators' responsibility.

665 *Study Drug Records*- It is the responsibility of the investigator to ensure that the 666 unblinded study coordinator maintains a current disposition record of investigational product. 667 Records or logs must comply with applicable regulations and guidelines and should include:

- 668
- 669

672 673

674

675

- amount received and placed in storage area; amount currently in storage area
- label ID number or batch number
- amount dispensed to and returned by each subject, including unique subject
 identifiers
 - non-study disposition (e.g., lost, wasted)
 - amount destroyed at study site

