For all analyses, in which the measures are continuous, data from evaluable subjects will be submitted to a repeated-measures general linear model (SS/ Drug treatments x repeated measures ANOVA) including the arm of drug treatment (liraglutide 3mg vs. placebo) as the between-subjects effect, and the visit (baseline and 30 wks) as the within-subjects effect. To evaluate the differences in the response to each treatment over visits, the interaction effect will be calculated. Baseline comparisons between groups will be made by one-way ANOVAs.

Frequency of patients achieving a body weight reduction of at least 5% and 10% before and after treatment will be compared with the McNemar test (complex chi square $[\chi^2]$ for paired data), which formally tests for a change between the observed proportions of k related samples. Dysglycemia occurrence before and after different treatment will also be compared with the McNemar test. The difference in frequency of menstruation before and aftertreatment will also be compared using the McNemar test.

Data will be analyzed on completed treatment parameters where relevant (evaluable population). The evaluable population is defined as all randomized subjects who complete treatment through week 30-32 week. Results will be reported as mean +/- S.E.M for normally distributed data and as median (interquartile range) if the distribution is not normal. Categorical data will be presented as percentage. P < 0.05 is considered statistically significant.

773

774 Sample Size and Justification

775 A priori sample size analysis was performed using the online calculator provided by the 776 Hospital Mallinckrodt General Clinical Massachusetts General Research Center (http://hedwig.mgh.harvard.edu/sample size/size.html). To calculate sample size, we used the 777 778 standard formula suggested for clinical trials by considering a type one error (α) of 0.05 and type 779 two error (β) of 0.20 (power = 80%). Sample size calculation revealed that 57 participants 780 randomized in a 2:1 ratio (liraglutide: placebo) were needed. Using a 30% drop-out rate, the 781 study is designed to recruit 92 patients, enroll 48 liraglutide and 24 placebo to ensure that the 782 number of subjects completing the study (38 LIRA/19 PL) as derived by the sample size 783 calculation is met.

784

785 Ethical and Regulatory Requirements

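### Menstrual frequency, an annualised count, is tested before versus after with McNemar: no cut-off, no liraglutide-versus-placebo contrast, and a baseline taken from the history used to select the women

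*Combined protocol and SAP*

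**What the plan says.** All places are in the combined protocol and SAP.

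- **Secondary endpoints, Anthropometric and Clinical Indices:** "Change in menstruation frequency (normalized to the number of menstruations per year) from before and after 30 weeks of treatment". The secondary objective is worded as anti-obesity medication versus placebo and includes clinical parameters.
- **Subjects (before value):** a gynaecological history is taken "with recording of menses in the 12-month period" before the study, and "Patients will be specifically asked about the number of menses in previous 12" months. No other pre-treatment count and no diary run-in is described.
- **Subjects (eligibility):** women must have "irregular periods (cycle length outside 24–35 days or <8 cycles per year").
- **Study Assessments (after value):** "During the study period, cycle control will be assessed daily by the subjects using a menstrual diary". The 30-week result is "normalized to the number of menstruations per year (52 weeks").
- **Statistical Methods (test):** "The difference in frequency of menstruation before and aftertreatment will also be compared using the McNemar test". The same section describes an arm-by-visit repeated-measures model for continuous measures. Menstrual frequency is not in its list of dependent variables.

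**The concern.** The endpoint and its test do not fit together, in three ways.

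1. McNemar works on a paired yes/no variable. The endpoint is a count per year, and the plan gives no threshold that would turn it into yes/no. The test cannot be run without a choice that has not been pre-specified.
2. McNemar asks whether women changed. It does not ask whether they changed more on liraglutide than on placebo, which is the objective.
3. The before value is the history on which women qualified as irregular, and the after value comes from a different instrument. Women selected for a low or irregular count will on average look better when counted again, even untreated. Any systematic gap between a 12-month history and a daily diary is added to that. A before/after test counts both as change on treatment.

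At stake is a claim that menstrual function improved which would not need a drug effect to arise, in a trial whose placebo arm could settle the question.

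**Working it through.** **Inputs.** From the documents: 38 liraglutide and 19 placebo completers (Sample Size and Justification), P < 0.05, a 30-week diary, scaling to 52 weeks, and fewer than 8 cycles per year as one route to eligibility. The documents give no menstrual rate, variance, recall error or McNemar cut-off, and no design figure for this endpoint to reproduce. The following are therefore assumptions: a mean of 6 menses per year; true rates varying between women as a gamma distribution with shape 2, 4 or 9; Poisson counts given each woman's rate; a cut-off of 8 per year; two-sided tests; and no drug effect.

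**Scaling.** 52/30 = 1.733. Four diary menses give 4 × 1.733 = 6.93 per year and five give 8.67, so a single bleed decides which side of 8 a woman falls on. The scaling does not bias the mean rate, but it makes a dichotomised endpoint coarse.

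**Regression to the mean.** With gamma shape 4 and mean 6, a woman who reports k menses in a year has expected true rate (4 + k)/(4/6 + 1) = (4 + k)/1.667.

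- k = 3: 7/1.667 = 4.2, an expected rise of 1.2.
- k = 5: 9/1.667 = 5.4, a rise of 0.4.
- k = 7: 11/1.667 = 6.6, a fall of 0.4.

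Averaged over women with k below 8, the spurious rise is about 0.8 menses per year, with accurate recall and no treatment effect.

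**Effect on McNemar.** If every woman starts below 8, crossings can only be upward. With m upward crossings the exact two-sided p-value is 2 × 0.5^m: 0.0625 for m = 5 and 0.031 for m = 6. Six crossings among 38 women are therefore enough. As a check without between-woman variation, suppose that all women share one true rate and all are classed below 8 at entry. Crossing then means at least 5 menses in 30 weeks:

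| True rate per year | Expected in 30 weeks | P(at least 5) | Expected crossers of 38 | P(McNemar significant) |
|---|---|---|---|---|
| 4 | 2.31 | 0.085 | 3.2 | 10% |
| 5 | 2.88 | 0.166 | 6.3 | 62% |
| 6 | 3.46 | 0.267 | 10.1 | 96% |

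**Gamma-Poisson simulation, all women selected on fewer than 8, recall exact, 38 women:**

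- paired t-test: falsely significant about 21-33% of the time across the gamma shapes;
- exact McNemar at 8 per year: about 46-87%;
- between-arm test, 38 versus 19: about 5%.

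This is an upper case, because a woman may also qualify on cycle length outside 24-35 days with 8 or more menses a year.

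**Instrument difference alone, no selection.** If the history under-reports by 10%, exact McNemar at 8 per year is falsely significant in about 3-6% of trials with 38 women and 1-3% with 19. At 20% under-reporting the figures are about 11-20% and 2-6%. If the history over-reports by 10%, a paired t-test in 38 women shows a false decrease about 13-14% of the time, which would hide a benefit. The between-arm test stays near 5%, because the shift is common to both arms.

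**The case against.** The strongest reply is that the plan already compares arms. The secondary objective is versus placebo, and the Statistical Methods section applies an arm-by-visit interaction to continuous measures. An annualised frequency is numeric and could be analysed that way. This makes the plan ambiguous, but does not rescue it: menses are missing from the dependent-variable list and are assigned by name to McNemar.

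A second reply is that the baseline may not be pure recall. Medical records are obtained to confirm the medical history, and no sentence states that the 12-month count is the baseline for this endpoint. That is fair. It is, however, the only pre-treatment count described, and regression to the mean would remain if the history were perfectly accurate.

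Third, this is one of many secondary endpoints, and the size of the error depends on assumed rates. Both points stand.

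A reader might infer more than the documents support:

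- **That the artefact favours liraglutide because its arm is larger.** This needs McNemar to be run separately in each arm, which the plan does not say. The expected spurious change is the same in both arms; only the chance of within-arm significance depends on arm size. Pooling would remove the arm-size argument but not the problem, since all 57 women would still be tested against their own selected baseline.
- **That the change from history to diary inflates benefit.** The documents give neither the size nor the direction of any recall error.
- **That the diary categories are defective because a two-pad day fits both.** Spotting is defined as "spotting (requiring at least one pad/tampon per day") and bleeding as two or more, but the text offers them as alternatives, so they are evidently meant to be exclusive. Nothing in the documents supports a rule that only bleeding days count towards a menstruation.

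**Conclusion.** The concern holds for the test, the missing arm contrast and the selected baseline. As written, the McNemar test for menses lacks the cut-off it needs, does not address the versus-placebo objective, and would count regression to the mean and any difference between history and diary as change on treatment. The 21-33% (paired t-test) and 46-87% (exact McNemar) false-positive rates are upper-case illustrations. They rest on a mean of 6 per year, gamma-Poisson variation, a cut-off of 8 and selection of every woman on fewer than 8 per year. The true rates could be much lower if many women qualify through cycle length instead. That a comparison between randomised arms avoids the problem does not depend on these figures. The documents do not support a claim that the error favours liraglutide, or that imperfect recall is its main source. The primary endpoints are unaffected.

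**What to change.** Replace the McNemar test for menses with a between-arm comparison of diary-counted menses during treatment. Use a negative-binomial model, or a Poisson model with standard errors that allow for overdispersion, since rates will differ between women. Include treatment arm, log of diary-weeks observed as offset, and the 12-month baseline frequency as covariate. Report the liraglutide-to-placebo rate ratio with its 95% CI. The offset replaces the 52/30 scaling and handles women observed for 28 rather than 30 weeks. State that the 12-month history is the baseline value, and present before/after change by arm descriptively, without a test.

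The cost is a few sentences of SAP text. All the data are already planned, and neither visits nor sample size change.

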729 Several other endpoints will be assessed at each study visit. Baseline blood samples will 730 also be collected for measurement of lipid profiles (cholesterol, HDL and LDL cholesterol, and triglycerides), adrenal androgens (DHEAS), and liver enzymes (AST/ALT). Dyslipidemia is defined
as the presence of at least one of the mentioned lipid parameters abnormalities.

733 Safety assessments

The safety and tolerability assessments will include incidence and intensity of adverse events, withdrawals because of adverse events, physical exams, vital sign measurements and clinical laboratory parameters. Patients will be seen at 16-18 weeks and 30-32 weeks for laboratory evaluation for a complete chemistry profile and to confirm they are not pregnant. Patients will also be required to perform monthly home pregnancy tests.

739 STATISTICAL/ANALYTICAL PLAN

740 Statistical Methods

Statistical analysis will be performed using SPSS version 15.1 for Windows (SPSS, Inc.; 741 742 Chicago, IL). Continuous variables will be tested for normality of distribution using the Kolmogorov-Smirov test. When necessary, non-normally distributed data will be subjected to 743 logarithmic or square-root transformation to obtain a normal distribution where necessary for 744 subsequent analyses. The primary endpoints are comparison of percent change in body weight 745 and therapeutic impact on biochemical hyperandrogenism (as determined by FAI) from baseline 746 747 to week 30 of treatment. The secondary endpoints include changes in surrogate measures of insulin action (HOMA-IR, SI_{OGTT}, IGI/HOMA-IR and IS-SI) and glycemic parameters (fasting blood 748 glucose [FBG] and 2 hour post OGTT glucose), glucose and insulin AUC, and mean blood glucose 749 (MBG), anthropometric parameters (BMI, absolute weight, WC and fat distribution by DXA), 750 751 blood pressure, lipid profiles, and adrenal androgen levels (DHEAS). Direct and indirect estimates of insulin sensitivity and secretion (HOMA, SI_{OGTT}, IGI/HOMA, β-cell compensatory 752 753 function, glycemic parameters (FBG, MBG, 2 hour post OGTT glucose level, AUC) anthropometric 754 measurements (body weight, BMI), fat distribution (WC, WHR and WHtR), BP, androgen and 755 lipid profiles will be considered as dependent variables.

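### The plan does not fix the scale on which the continuous co-primaries are tested: a small gap for percent weight change, a moderate and avoidable power loss for the free androgen index

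*Combined protocol and SAP*

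**What the plan says.** Under Primary endpoints, 1a is "percent change in body weight from baseline to week 30" and endpoint 2 is the reduction in FAI. Under Secondary endpoints the list opens with "Change from baseline of body mass index [BMI], absolute body weight, waist circumference". Statistical Methods repeats the split: "The primary endpoints are comparison of percent change in body weight", together with "therapeutic impact on biochemical hyperandrogenism (as determined by FAI) from baseline" to week 30, while the secondary list has "anthropometric parameters (BMI, absolute weight, WC and fat distribution by DXA".

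The same section then lists the dependent variables, including "measurements (body weight, BMI), fat distribution (WC, WHR and WHtR), BP, androgen and" lipid profiles. Percent change is not on that list. One model serves all continuous measures: a repeated-measures general linear model with arm between subjects "and the visit (baseline and 30 wks) as the within-subjects effect", with the response to treatment judged by the interaction.

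On scale, the section says "Continuous variables will be tested for normality of distribution using the" Kolmogorov-Smirnov test, with a log or square-root transformation where needed. It does not say which visit is tested, whether the test is corrected for an estimated mean and SD, or when log is preferred to square root. Results are to be given as mean and standard error, or as median and interquartile range. No between-arm estimate with a confidence interval is requested.

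**The concern.** With two visits, the interaction tests the change score of whatever variable is entered. Percent change has no natural baseline value, so it does not fit the model unless weight is re-expressed, for example as percent of baseline, and the plan does not say to do that. An analyst who follows the list literally would enter kilograms and could report the p-value for a secondary endpoint as that for 1a.

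For FAI no sentence fixes the scale at all. FAI is a ratio and may be skewed, so raw and log tests can have quite different power, and a test with little sensitivity at 57 patients would make the choice. What is at stake is mainly power on a co-primary endpoint, and a reported effect whose scale is known only after the data are seen.

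**Working it through.** **Inputs from the documents.** 38 liraglutide and 19 placebo completers (57), 2:1 allocation, alpha 0.05, power 80% (Sample Size and Justification). No effect size, SD, correlation or endpoint is given, so every other input below is an assumption.

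**The plan's own figure.** 57 cannot be reproduced forwards. Solved backwards, two-sided, the standardised difference is (1.960 + 0.842) × √(1/19 + 1/38) = 2.802 × 0.281 = 0.79 (0.80 with the t distribution). That fits any scale, so the sample size does not show which was meant.

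**Identity.** Let D be the week-30 value minus the baseline value for each woman. The interaction F on (1, 55) degrees of freedom equals the squared two-sample t on D. In one simulated 38/19 data set:
- kg: F = t² = 6.308.
- Percent change: t² = 7.727. The planned interaction gives the same 7.727 when baseline is set to 0 for everyone.
- Log weight: F = 7.760.

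So the model can test percent change exactly, but only if it is given that variable.

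**Size for 1a** (40,000 trials per setting; baseline mean 110 kg, placebo change -2%, arm difference 4.8 points, SD 6 points, so 4.8/6 = 0.80):

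| Baseline SD | kg and percent verdicts differ, effect constant in percent | Same, effect constant in kg |
|---|---|---|
| 15 kg | 3.9% | 3.9% |
| 20 kg | 5.1% | 5.4% |
| 25 kg | 6.7% | 7.0% |

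Power is 76.8-80.2% on kg and 76.3-79.9% on percent. Type I error is 4.8-5.0% on each scale. A separate run (mean 105 kg, SD 18, changes of -5% and -1%, SD 5 points) gave 4.3% disagreement.

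**Size for FAI: the scale rule.** Assume FAI is log-normal with log-SD 0.4-0.8 and baseline/week-30 correlation r of 0.5-0.9, and that the log change-score test has 80% power. Apply the normality test to baseline FAI, and use log when it rejects and raw otherwise:

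| Normality test | Power | Verdict differs from the log test |
|---|---|---|
| Uncorrected Kolmogorov-Smirnov | about 68-72% | about 9-14% of trials |
| Lilliefors-corrected | about 77-80% | about 0.5-5% of trials |

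The loss is 8-12 points or 0-3 points. A repeat run moved these ends by a point or less. The cause is sensitivity: at log-SD 0.4 and r = 0.7 the uncorrected test flags 6% of trials and the corrected one 59%. Testing either visit rather than baseline alone flags more often and loses less; at log-SD 0.8 the uncorrected disagreement can fall to about 2-3%. Type I error stays near 5% throughout.

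**Size for FAI: baseline as covariate.** Let k = week-30 SD / baseline SD. The ratio of error variances, ANCOVA to change score, is k²(1 - r²) / (1 + k² - 2rk). For k = 1 and r = 0.7 it is 0.51/0.60 = 0.85. ANCOVA power where the change score has 80%:

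| k | r = 0.5 | r = 0.7 | r = 0.9 |
|---|---|---|---|
| 0.7 | 98% | 98% | 99% |
| 1.0 | 89% | 85% | 81% |
| 1.3 | 82% | 79% | 83% |

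These use ordinary standard errors and equal spread in the two arms.

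**Unequal spread under 2:1** (normal data; k = 0.7 treated, 1.0 placebo; equal mean change). Ordinary ANCOVA rejects in about 7-9% of null trials, the change score in 4.5-6.1%, and ANCOVA with HC3 errors in about 5%. In that setting HC3 ANCOVA has 83-91% power against 79-82% for the change score. Where spread is in fact equal, a check on the nine settings of the table (40,000 trials each) found that HC3 costs up to about 2 points of power compared with ordinary errors. In the least favourable cell (k = 1.3, r = 0.7) power falls from about 79.5% to 77.7%.

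**The case against.** The strongest reply is that the scale of 1a is stated twice, once inside Statistical Methods itself. The dependent-variable list names measurements rather than analysis scales, and body weight has to appear there because absolute weight is secondary. This stands: percent change is clearly the intended endpoint, and one clarifying phrase closes the gap. A reader might infer that the trial will test the wrong primary endpoint. The documents do not support that; they only fail to say how the named endpoint enters the model.

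On FAI, the reply is that the plan already transforms skewed data. This stands in part. Comparing an always-raw with an always-log test would overstate the problem, because the plan does neither, and with a Lilliefors correction little is lost. But the plan does not specify that correction, and without it the loss is material.

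A reader might also infer inflated false positives, or that leaving out baseline FAI is a mistake. Neither follows. Following the rule mechanically keeps type I error near 5%; inflation would need an analyst to depart from the plan and pick among scales. The change-score interaction is a valid test, and omitting the covariate usually costs precision only.

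Finally, ordinary ANCOVA can do worse than the planned test when spread differs between arms under 2:1 allocation, and this is true on the log scale as well as the raw one. That stands in full, so the robust variance belongs to the recommendation on whichever scale is used.

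**Conclusion.** The concern holds as a gap in specification, not as an invalid analysis. For 1a it is minor: the model and the listed variable lead literally to kg change, but the verdict would differ from that on percent change in only about 4-7% of trials. For FAI it is moderate: letting a normality test choose the scale costs about 8-12 points of power uncorrected or 0-3 points with Lilliefors, and leaving out baseline FAI forgoes a gain that runs from large to none. The FAI figures rest on assumed log-normality, SDs and correlations, since the documents give none. The two-visit identity rests on no such assumption.

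**What to change.** Before unblinding, add to Statistical Methods:

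1. Endpoint 1a is analysed as untransformed percent weight change from baseline to week 30, compared between arms.
2. The FAI scale is fixed in advance (for example log, reported as a ratio), with no normality test deciding it. Week-30 FAI is analysed by ANCOVA on arm and baseline FAI, with heteroscedasticity-robust standard errors (for example HC3) on whichever scale is used.
3. The between-arm difference or ratio is reported with a 95% confidence interval.

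The cost is wording only. ANCOVA belongs to the same family of general linear models as the planned analysis, and testosterone and SHBG are already measured at baseline. It uses one degree of freedom. The covariate costs at most about 1 point of power in the least favourable setting tried, and HC3 up to about 2 points compared with ordinary errors when spread is equal. A log analysis also means that the FAI effect is read as a ratio.
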